### 4.2.3 Microbiological Intent-to-treat population

The mITT population consists of all patients in the ITT population with a causative pathogen identified at baseline.

### 4.2.4 Microbiologically Evaluable population

The ME population consists of all patients in the CE population with a causative pathogen identified at baseline and a microbiological outcome assessment at the TOC visit.

### 4.2.5 Pharmacokinetic population

The PK population consists of all patients who received at least one dose of ceftobiprole and had at least one sample of plasma concentration measurement obtained by the appropriate methodology.

## 4.3 Other important considerations

### 4.3.1 Definition of baseline

Unless otherwise specified, baseline is defined as the last non-missing assessment prior to the first study drug administration. Both scheduled and unscheduled visits and assessments will be used in determining baseline.

### 4.3.2 Definition of infecting organism (i.e., pathogen)

The identification of organisms as infecting (i.e., pathogen) or non-infecting is based on Investigator assessment as reported in the eCRF. The assessment may be based on blood samples, urine, cerebrospinal fluid, or any other suitable specimen samples.

When multiple samples from the same specimen are taken on a specific study day and isolates are not all sent for central microbiology testing, or when local and central identification differ, only the results from the central microbiology laboratory on that study day will be considered for the identification of organisms.

A causative pathogen is an infecting organism confirmed by central identification.

#### 4.3.3 Study day calculation and visit windows

Visit windowing approaches will not be used for this study, and visit-based summaries will include scheduled assessments only. If more than the specified number of measurements has been taken in a scheduled visit, the latest recorded values will be used in visit summaries, unless otherwise stated. All scheduled and unscheduled post-baseline assessments will be used for derivation of minimum and maximum post-baseline values. If more than one assessment has the same minimum or maximum value, then the record with earliest occurrence will be selected respectively as the minimum or maximum assessment.

The following conventions will be used to calculate analysis study day:

- Day 1 is the day of first study drug administration. Day -1 is the day before Day 1. No Day 0 is defined for this study.
- Prior to Day 1, the algorithm is:  
Study Day = visit/examination date – date of first study drug administration
- For Day 1 and subsequent days, the algorithm is:  
Study Day = visit/examination date – date of first study drug administration + 1.

Summary data such as AEs and concomitant medications will not be reported by visit. Tables that report abnormalities (e.g., clinically-notable abnormalities, laboratory shift tables) will include all assessments.

#### 4.3.4 Missing and partial data

The following rules for missing data will be followed:

- Adverse event and prior/concomitant medication date imputations will follow the rules described in [Appendix 1](#).
- The causality assessment for AEs should not be missing and will be queried for a value. Adverse events with missing causality will be considered related to study drug.
- For ACM through Day 28, patients with unknown survival status will be considered deceased for the efficacy outcome. If it is known that the patient died but death date is unknown, then the death date will be imputed to last date known to be alive +1 day.
- Unless otherwise specified, missing values for other individual data points will remain as missing. Missing values will not be imputed, and only observed values will be used in data analyses and presentation.

#### 4.3.5 Duration (e.g., for adverse events)

If date and time are collected, then duration is calculated as event end date and time minus event onset date and time. Duration will be displayed as days and fractions of days, or as hours and fractions of hours, as appropriate.

If only the date is collected, then the duration in days is calculated as event end date minus event onset date + 1.

#### 4.3.6 Coding dictionaries

Adverse events and medical history are to be coded using the Medical Dictionary for Regulatory Activities (MedDRA) Version 25.1 or later. Previous and concomitant treatments are to be coded using the World Health Organization Drug Dictionary Enhanced (WHO DDE) dated 01MAR2024 or later (format B3).

### 5 PATIENT DISPOSITION

#### 5.1 Disposition

The following analysis sets will be summarized: patients in the ITT/Safety population, patients enrolled but never dosed, patients in the CE population, patients in the mITT population, patients in the ME population, and patients in the PK population. All percentages will be based on the number of patients in the ITT population. Patients who failed screening, and the reasons for screen failure, will be listed only.

Patient disposition (treatment, EOT, TOC, and LFU) will be summarized for the ITT population.

#### 5.2 Protocol deviations

A protocol deviation is any change, divergence, or departure from the study design or procedures defined in the protocol. Protocol deviations will be documented by the clinical monitor throughout the course of monitoring visits. The protocol deviations will be categorized as important and non-important deviations, with important deviations further classified as major or minor (see the definition of the CE population in Section 4.2.2).

All protocol deviations will be listed, with patients with major protocol deviations leading to exclusion from CE population identified prior to database lock.

#### 5.3 Inclusion and exclusion criteria

Full inclusion and exclusion criteria are listed in protocol Section 4.2 and 4.3, respectively. Data for inclusion/exclusion criteria for each patient will be listed.

## 6 DEMOGRAPHICS AND BASELINE CHARACTERISTICS

### 6.1 Demographics and general baseline characteristics

The following demographics and baseline characteristics data will be presented in tables using descriptive statistics for the ITT, CE, mITT, and PK populations:

- Post-natal age, gestational age, breastfed by lactating mother status, sex, race, ethnicity
- Height, weight.

### 6.2 Medical history

Medical history will be summarized overall and for each System Organ Class (SOC) and Preferred Term (PT), for the ITT population.

## 7 TREATMENTS AND MEDICATIONS

### 7.1 Prior and concomitant medications

All medications, other than the study drug, used during the study (from 7 days prior to the first dose of study drug, or from 3 days prior to the first dose of study drug for medications taken by the lactating mother), must be documented on the appropriate section of the eCRF.

Prior medications are defined as medications with a stop date prior to the first dose of study drug. Concomitant medications are defined as medications that are either ongoing at the time of the first dose of study drug, or start after the first dose of study drug.

The number and percentage of patients who receive prior and/or concomitant medication will be summarized separately by ATC level 2, ATC level 4, and PT.

At each level of summarization, a patient is counted once if he/she reports one or more medications at that level. All prior medications and concomitant medications will be summarized for the ITT population.

The imputation algorithm for partial concomitant medication dates is provided in [Appendix 1](#).

### 7.2 Concomitant procedures

Concomitant procedures are defined as procedures that are either ongoing on the time of the first dose of study drug, or with a start date missing, or start after the first dose of study drug. All concomitant procedures will be listed.

### 7.3 Study treatments

#### 7.3.1 Study drug exposure

Duration of study drug therapy and compliance will be summarized for the Safety population.

- Study drug duration is defined as:

Days of (Date and time of the last dose – Date and time of first dose), rounded to one decimal.

- Compliance is defined as:

Actual total dose (mg) / Planned total dose (mg)

Compliance will be classified into one of the categories < 80%, 80–120%, or > 120%, and will be presented as the number and percentage of patients in each category for the Safety population.

### 7.3.2 Study drug administration

All study drug administration data will be listed.

## 8 EFFICACY ANALYSIS

### 8.1 Overall clinical outcome

Overall clinical outcome is to be assessed at the EOT and TOC visits by the Investigator as ‘Clinical cure’, ‘Clinical failure’, or ‘Unevaluable’ (see protocol Section 5.6.1 for details). Clinical cure rate and reasons for failure or unavailability of data will be summarized in a table for the ITT and CE populations.

### 8.2 All-cause mortality through Day 28

Vital status is to be assessed at the LFU visit, in person or by telephone contact. Patients will be considered to have died at Day 28 if they meet all the following criteria:

- A death is reported on the eCRF
- The study day for death is  $\leq 28$ .

The ACM at Day 28 will be summarized in a table for the ITT population.

### 8.3 Microbiological response

Microbiological outcome is to be assessed at the EOT and TOC visits by the Investigator as ‘Eradication’, ‘Presumed eradication’, ‘Persistence’, ‘Presumed persistence’, ‘Unevaluable’, or ‘Relapse’ (see protocol Section 5.6.3 for details). If applicable, the relapse status of the patient is to be assessed at the LFU visit, by the Investigator.

Patients will be considered to have experienced microbiological eradication if they are classified as ‘Eradication’ or ‘Presumed eradication’. Microbiological eradication at EOT and TOC, and relapse status at the LFU visit, will be summarized in a table for the mITT and ME populations.

All microbiological data will be listed.

### 8.4 Signs and symptoms of late-onset sepsis

Signs and symptoms of LOS are to be assessed by the Investigator as ‘Present’, ‘Absent’, ‘Improved’, ‘Unchanged’, or ‘Worsened’.

Overall signs and symptoms assessment will be derived and summarized at Day 3, EOT, and TOC, for the ITT and CE populations. The following rules will be applied for categorization:

1. Each post-baseline sign or symptom evaluation is re-classified as stated in the following table:

| Baseline | Post-baseline |          |          |           |          |
|----------|---------------|----------|----------|-----------|----------|
|          | Present       | Absent   | Improved | Unchanged | Worsened |
| Present  | Unchanged     | Resolved | Improved | Unchanged | Worsened |
| Absent   | Worsened      | Absent   | NA       | Absent    | Worsened |

2. Overall assessment for each visit is derived as follows:

- Resolved: all signs and symptoms are classified as ‘Resolved’ or ‘Absent’ (see table above).
- Improved: all signs and symptoms are classified as ‘Resolved’ or ‘Improved’ or ‘Absent’ (see table above), with at least one ‘Improved’.
- Unchanged: all signs and symptoms are classified as ‘Resolved’, ‘Improved’ or ‘Unchanged’ or ‘Absent’ (see table above), with at least one ‘Unchanged’.
- Worsened: there is at least one sign or symptom classified as ‘Worsened’.

All signs and symptoms data will be listed.

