### 4.2 Inclusion criteria

For inclusion in the study, patients must meet all of the following criteria:

1. Informed consent from parent(s) or other legally-acceptable representative (LAR) to participate in the study
2. Male or female, with a gestational age of  $\geq$  24 weeks and a post-natal age ranging from  $\geq$  3 days to  $\leq$  3 months
3. Diagnosis of documented or presumed bacterial LOS requiring administration of IV antibiotic treatment.

Patients must present with at least two of the clinical criteria and at least one of the laboratory criteria listed below:

Clinical criteria (at least two):

- a) Hypothermia ( $< 36.6^{\circ}\text{C} / 97.9^{\circ}\text{F}$  rectal;  $< 36.5^{\circ}\text{C} / 97.7^{\circ}\text{F}$  axillary;  $< 35.5^{\circ}\text{C} / 95.9^{\circ}\text{F}$  oral;  $< 35.8^{\circ}\text{C} / 96.4^{\circ}\text{F}$  tympanic) OR fever ( $> 38.0^{\circ}\text{C} / 100.4^{\circ}\text{F}$  rectal;  $> 37.5^{\circ}\text{C} / 99.5^{\circ}\text{F}$  axillary;  $> 37.5^{\circ}\text{C} / 99.5^{\circ}\text{F}$  oral;  $> 38.0^{\circ}\text{C} / 100.4^{\circ}\text{F}$  tympanic)
- b) Bradycardia ( $< 100$  beats/minute awake;  $< 80$  beats/minute asleep) OR tachycardia ( $> 205$  beats/minute awake;  $> 160$  beats/minute asleep)
- c) Urinary output  $0.5\text{--}1\text{ mL/kg/h}$  OR hypotension OR signs of impaired peripheral perfusion, such as mottled skin, moist and cold skin, finger to forearm temperature gradient, or increased capillary refill time
- d) Petechial rash OR sclerema neonatorum
- e) New onset or worsening of apnea episodes OR tachypnea episodes OR increased oxygen requirements OR requirement for ventilatory support (excluding underlying ventilator-associated pneumonia; see exclusion criteria)
- f) Feeding intolerance OR poor sucking OR abdominal distension
- g) Irritability
- h) Lethargy
- i) Muscular hypotonia

*Laboratory criteria (at least one):*

- a) White blood cell count  $\leq 4.0 \times 10^9/\text{L}$  OR  $\geq 20.0 \times 10^9/\text{L}$
- b) Immature to total neutrophil ratio  $> 0.2$
- c) Platelet count  $\leq 100 \times 10^9/\text{L}$
- d) C-reactive protein  $> 15 \text{ mg/L}$  OR procalcitonin  $\geq 2 \text{ ng/mL}$  OR Interleukin-6 (IL-6) elevated according to local laboratory thresholds
- e) Hyperglycemia OR hypoglycemia
- f) Metabolic acidosis

4. Sufficient vascular access to receive study drug and to allow blood sampling at a site separate from the study drug infusion line

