#### **4.3 Exclusion criteria**

Patients who meet any of the following criteria must be excluded from the study:

1. History of a previous clinically relevant hypersensitivity or serious adverse reaction to beta-lactam antibiotics, or to aminoglycosides if intended to be used in combination with ceftobiprole
2. Viral, fungal, or parasitic pathogen as the sole reason for infection, OR known resistance of the causative bacterial pathogens to ceftobiprole
3. Refractory septic shock not responding to 60 minutes of vasopressor treatment within 48 hours before enrollment
4. Proven ventilator-associated pneumonia
5. Proven central nervous system infection (e.g., meningitis, brain abscess)
6. Proven osteomyelitis, infective endocarditis, or necrotising enterocolitis
7. Impaired renal function or known significant renal disease, as evidenced by an estimated glomerular filtration rate (using the Schwartz formula or other applicable formula) calculated to be less than 2/3 of normal for the applicable age group, OR urinary output  $< 0.5 \text{ mL/kg/h}$  (measured over at least 8 hours), OR requirement for dialysis
8. Significant laboratory abnormalities, including:
  - a) Hematocrit  $< 20\%$
  - b) Absolute neutrophil count  $< 0.5 \times 10^9/\text{L}$
  - c) Alanine aminotransferase (ALT) or aspartate aminotransferase (AST)  $> 8 \times$  the age-specific upper limit of normal
9. Progressively fatal underlying disease, or life expectancy  $< 30$  days
10. Documented history of convulsions

11. Severe immunodeficiency (congenital or acquired)
12. Use of systemic antibacterial therapy for longer than 72 hours within 7 days before start of study medication
13. Any condition including antepartum / peripartum factors or procedures, which would, in the opinion of the Investigator, make the patient or caregiver unsuitable for the study, putting the patient at risk or compromising the quality of the data
14. Participation in another clinical study with an investigational product within 30 days of enrollment in the current study

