### 5.2.1 Screening visit / Baseline (Day –2 to Day 1)

The following assessments and procedures will be performed at the screening visit (Day –2 to Day 1; see Table 3):

- Medical history and demographics, including the antepartum/peripartum period (see Section 5.3.1)
- Review and recording of medications taken within 7 days before the first dose of study drug. For patients who are being breastfed, medications taken by the lactating mother within 3 days before the first dose of study drug will also be recorded.
- Physical examination (see Section 5.5.2)
- Length and body weight (see Section 5.5.2)
- Vital signs (including body temperature, respiratory rate, pulse rate, and systolic and diastolic blood pressures) and pulse oximetry (see Section 5.5.3)
- Signs and symptoms of LOS (see Section 5.6.4)
- Local laboratory tests: results will be used for the assessment of inclusion/exclusion criteria and throughout the study (for details, see Sections 4.2, 4.3, and 5.5.4). Laboratory tests required as part of the screening process which have been performed within 48 hours prior to the first dose of study drug do not need to be repeated, regardless of whether they were performed before or after signing of the informed consent form (ICF).
- If clinically indicated, measurement of urine output (over at least an 8-hour period) in patients hospitalised  $\geq$  8 hours before study drug dosing. Use of a urinary catheter is based on the Investigator's judgement in accordance with local standard of care. Urinary catheters are not required for the purposes of this study.
- Recording of results of imaging studies (e.g., chest X-ray, ultrasound, CT scan, MRI) performed as part of the patient's standard of care within 72 hours before the first dose of study drug.
- Collection of blood and other specimens for microbiological evaluation as clinically indicated based on the Investigator's judgement in accordance with local standard of care (see Section 5.4)

The Investigator will review the results of the screening assessments and procedures, including results of laboratory tests, and all inclusion/exclusion criteria to ensure patient eligibility.

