#### **5.6.5 Signs and symptoms of LOS**

The Investigator must rate the following signs and symptoms of LOS as:

- 'absent' or 'present' at baseline (pre-dose)
- 'absent', 'improved', 'unchanged' or 'worsened' compared to baseline, on every day of active study treatment, and at the EOT, TOC, and LFU visits

1. Fever ( $> 38.0^{\circ}\text{C} / 100.4^{\circ}\text{F}$  rectal;  $> 37.5^{\circ}\text{C} / 99.5^{\circ}\text{F}$  axillary;  $> 37.5^{\circ}\text{C} / 99.5^{\circ}\text{F}$  oral;  $> 38.0^{\circ}\text{C} / 100.4^{\circ}\text{F}$  tympanic)
2. Hypothermia ( $< 36.6^{\circ}\text{C} / 97.9^{\circ}\text{F}$  rectal;  $< 36.5^{\circ}\text{C} / 97.7^{\circ}\text{F}$  axillary;  $< 35.5^{\circ}\text{C} / 95.9^{\circ}\text{F}$  oral;  $< 35.8^{\circ}\text{C} / 96.4^{\circ}\text{F}$  tympanic)
3. Abnormal heart rate
  - a. Bradycardia ( $< 100$  beats/minute awake;  $< 80$  beats/minute asleep)
  - b. Tachycardia ( $> 205$  beats/minute awake;  $> 160$  beats/minute asleep)
4. Signs of impaired circulation
  - a. Urine output  $0.5\text{--}1$  mL/kg/h (in patients with urinary catheters; note: urinary catheters are not required for the purposes of this study)
  - b. Hypotension
  - c. Signs of impaired peripheral perfusion, such as mottled skin, moist and cold skin, finger to forearm temperature gradient, or increased capillary refill time
5. Petechial rash OR sclerema neonatorum
6. Respiratory distress
  - a. New onset or worsening of apnea episodes
  - b. Tachypnea episodes
  - c. Increased oxygen requirements
  - d. Requirement for ventilatory support (note: proven ventilator-associated pneumonia is an exclusion criterion; see Section 4.3)
7. Gastrointestinal distress
  - a. Feeding intolerance
  - b. Poor sucking
  - c. Abdominal distension
8. Irritability
9. Lethargy
10. Muscular hypotonia

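### SAP 8.4 tabulates an infant with no LOS signs before the first dose, and none afterwards, as 'Resolved', because that category does not require any sign to have resolved

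*SAP*

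**What the plan says.** Protocol 5.6.5 has the investigator rate ten signs of LOS as absent or present before dosing, and afterwards as absent, improved, unchanged or worsened relative to baseline. SAP 8.4 re-classifies each sign from its baseline and later rating, then derives one overall category per visit. A sign absent at baseline and later rated 'Absent' or 'Unchanged' becomes 'Absent'. The overall rules are:

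- "Resolved: all signs and symptoms are classified as ‘Resolved’ or ‘Absent", with no further condition.
- 'Improved' adds that at least one sign must be 'Improved'.
- 'Unchanged' adds that at least one sign must be 'Unchanged'.
- "Worsened: there is at least one sign or symptom classified as ‘Worsened".

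This derivation serves a named secondary efficacy endpoint in the ITT and CE populations (SAP 3.2.2). Percentages use all patients in the population unless otherwise specified, and summaries are shown for term, pre-term and all infants (SAP 4).

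Four provisions decide whether an infant can have no signs at baseline:

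- Inclusion criterion 3: "Patients must present with at least two of the clinical criteria and at least one of the laboratory criteria listed below". It gives no time point.
- Screening/baseline runs from Day -2 to Day 1 (Protocol 5.2.1).
- In SAP 4.3.1, "baseline is defined as the last non-missing assessment prior to the first study drug administration", drawn from scheduled and unscheduled assessments.
- Exclusion criterion 12 bars "Use of systemic antibacterial therapy for longer than 72 hours within 7 days before start of study medication", so shorter courses are allowed.

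**The concern.** A category called 'Resolved' should mean that something present at baseline has gone. As written, it also takes in infants who had nothing to resolve when ceftobiprole started. The parallel conditions on 'Improved' and 'Unchanged' suggest an omission rather than a choice.

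The endpoint is meant to show change in signs after the first dose. The study is single-arm, so no comparator would reveal how much of the 'Resolved' column reflects infants already sign-free. At about eight patients, a single infant is visible in the percentage.

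There is also a gap in completeness. A baseline 'Absent' followed by 'Improved' is mapped to 'NA', and SAP 8.4 does not say what happens to that infant's overall category.

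**Working it through.** There is no planned figure to reproduce: the SAP states no expected rate and performs no hypothesis testing. The check applies the SAP 8.4 rules to rating patterns, asks whether the problem pattern can occur, and sizes its effect.

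**Step 1. Apply the rules to ten rated signs.**

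| Baseline | Post-baseline | Overall category under SAP 8.4 |
|---|---|---|
| All 10 absent | All 'Absent' | Resolved |
| All 10 absent | All 'Unchanged' | Resolved |
| All 10 absent | 9 'Absent', 1 new or worsened | Worsened |
| All 10 absent | At least one 'Improved', none worsened | None defined ('NA') |
| 1 present, 9 absent | The one 'Unchanged', the rest 'Absent' | Unchanged |

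The first two rows are the defect. The last row shows that partial recovery before baseline does not trigger it: one remaining unchanged sign gives 'Unchanged'. The fourth row is the 'NA' gap, which can also arise in an infant who has other signs at baseline.

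**Step 2. Can an all-absent baseline occur?** Criterion 3 draws on essentially the same list as the signs rated in Protocol 5.6.5. An infant meeting it therefore has at least one ratable sign at that moment, even if one of the two criteria was low urine output, which 5.6.5 rates only in catheterised infants. An all-absent baseline needs every qualifying sign to clear between the eligibility assessment and the last pre-dose rating. The missing time point in criterion 3, the Day -2 to Day 1 window and the last-assessment definition of baseline leave room for this. Several of the signs, such as fever, heart rate and apnoea episodes, can change quickly.

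**Step 3. Size.** Let N be the population, k the infants sign-free at baseline and afterwards, and r the number resolved among the other N - k.

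- Rate as written: (r + k) / N
- Rate among infants with at least one baseline sign: r / (N - k)
- Difference: k(N - k - r) / [N(N - k)]

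Each such infant adds 1/N to the tabulated percentage: 1/8 = 12.5 points overall, 1/6 = 16.7 points in the pre-term group and 1/2 = 50 points in the term group. These N are the planned minimum sizes. The difference between the two rates, with k and r assumed and N = 8, is:

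| k | r of N - k | As written | Restricted | Difference (points) |
|---|---|---|---|---|
| 0 | 4 of 8 | 4/8 = 50.0% | 4/8 = 50.0% | 0 |
| 1 | 4 of 7 | 5/8 = 62.5% | 4/7 = 57.1% | 5.4 |
| 2 | 4 of 6 | 6/8 = 75.0% | 4/6 = 66.7% | 8.3 |
| 2 | 3 of 6 | 5/8 = 62.5% | 3/6 = 50.0% | 12.5 |
| 2 | 6 of 6 | 8/8 = 100% | 6/6 = 100% | 0 |

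If instead one infant is sign-free at baseline and then develops a sign, that infant is 'Worsened' but still in the denominator. With 4 of the other 7 resolved, the table shows 4/8 = 50.0% against 4/7 = 57.1% among infants with baseline signs.

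**The case against.** The strongest reply is that the pattern should be rare. Criterion 3 demands clinical signs, Protocol 5.2.2 has dosing start as soon as possible after enrolment, and Table 3 places the eligibility check and the baseline sign rating in one combined column. A later pre-dose present/absent rating would be an exception, although SAP 4.3.1 would use it. The endpoint is secondary and descriptive, investigator-rated clinical cure does not use this derivation, and all sign ratings will be listed by patient. All of this stands and limits how much the point matters. It does not correct the table: the rule still gives the wrong label when the pattern occurs, and a listing leaves the reader to notice it.

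Several stronger readings are tempting, and the documents do not support them.

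- A reader might infer that recovery under up to 72 hours of earlier antibiotics is generally credited to ceftobiprole. If criterion 3 applies at enrolment, an infant fully recovered by then is ineligible. The route widens only if the criterion refers to onset of the episode, and the protocol does not say which. Nor does SAP 8.4 call 'Resolved' a ceftobiprole response; ampicillin and/or an aminoglycoside may be given alongside.
- The catheter limit on urine output might look like a second route to an all-absent baseline. Alone it is not, since two criteria are needed.
- The error might seem able only to favour the drug. That is true of the false 'Resolved' label, but a sign-free infant who develops a sign counts as 'Worsened'.
- The 12.5 points might be read as the bias per infant. It is the contribution to the tabulated percentage; the difference from the restricted rate varies, as shown above.

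On 'NA', it is fair to say that the cell flags an illogical rating and is mainly a data-cleaning matter. But 5.6.5 offers 'improved' for any sign after baseline, so the entry can occur and the SAP should say what follows.

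**Conclusion.** The point holds in a narrow form. SAP 8.4 lacks a condition on 'Resolved' that it places on the two neighbouring categories, so an infant sign-free at the last pre-dose assessment and afterwards is tabulated as 'Resolved' although no sign resolved after the first dose. The label is wrong by the rule itself; no assumption is needed for that.

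The practical size does rest on assumptions. The number of affected infants is not given and may be zero, in which case nothing changes. At N = 8 each adds 12.5 points to the tabulated 'Resolved' percentage. In the illustrations above, the excess over the restricted rate ranges from nothing to 12.5 points. The primary safety endpoint and the clinical cure rate are untouched.

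The 'NA' gap is separate and smaller: an infant with such a rating has no overall category unless another sign is 'Worsened'.

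**What to change.** Before database lock, amend SAP 8.4 as follows.

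1. Add to the 'Resolved' definition the condition 'with at least one Resolved'.
2. Add a category 'No signs at baseline, none since', shown as a count. An infant with no baseline signs who later develops one is still reported as 'Worsened'.
3. Beside the full-population table, give the resolved/improved rate among infants with at least one baseline sign, with its denominator.
4. Query any 'Improved' rating for a sign absent at baseline, and state how an 'NA' that remains after query enters the overall category.

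The cost is a few lines of SAP text and programming, with no new data collection. The resolved rate may come out slightly less favourable. If no infant is sign-free at baseline, the first three changes leave the results as they are.
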